10.2. Secondary/Exploratory Analyses

- **Within-group change over time:** Friedman two-way repeated measures ANOVA (pre, Day 0, Day 14, Month 7). Post-hoc Dunn-Bonferroni pairwise tests.
- **Between-group at Day 14 & Month 7:** Mann–Whitney U.

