STUDY PROTOCOL WITH STATISTICAL ANALYSIS PLAN

Study Title: Vaginal Breech Birth Management: serious mobile game design and evaluation for midwifery students

NCT Number: NCT05551611

Document Date: March 14, 2025

1. Background and Rationale

Vaginal breech birth (VBB) is now an infrequent clinical event; consequently, midwifery students have limited real-life learning opportunities. Serious games offer cost-effective, repeatable simulation experiences that can enhance knowledge acquisition. This study evaluates a bespoke mobile serious game designed to teach VBB management and compares it with traditional lecture-based instruction.

2. Aims

- To determine whether the serious mobile game improves short-term knowledge of VBB management compared with a traditional lecture.
- To compare knowledge retention at 14 days and 7 months post-intervention between groups.

3. Study Design

Prospective, parallel-group, randomised controlled quasi-experimental trial with pre-test/post-test assessments.

- **Setting:** Midwifery departments of two Turkish universities (Kocaeli University & Eskişehir Osmangazi University).
- **Duration:** February 2022 – December 2022 (follow-up to July 2023).

4. Study Population and Eligibility Criteria

Third-year midwifery students.

Inclusion:

- Completed “Normal Childbirth & Postpartum” course.
- Provide written informed consent.

Exclusion: Previous theoretical or practical training on breech presentation.

5. Interventions

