5.2. Control Arm – “Lecture Group”

Traditional 45-min lecture covering identical VBB content, delivered by the same investigator with slides & discussion.

6. Outcome Measures

Type	Name	Description	Scale (range)	Direction
Primary	Vaginal Breech Birth Management Knowledge Test	47-item multiple-choice test assessing knowledge of trauma & management in VBB. Each correct answer = 1 point; Total score 0–47 . No subscales; higher scores = better knowledge/outcome.	0–47 scores on a scale	Higher = better

Assessments at baseline (pre-test), Day 0 (immediately after intervention), Day 14, and Month 7.

7. Sample Size & Power Calculation

Using Day 0 pilot means (Game=40.5 \pm 4.2; Control=37.8 \pm 5.1), $\alpha=0.05$, two-sided Mann–Whitney U, power=0.80 required **n=35 per group**. Allowing 10 % attrition, recruitment target set at 40 per group (total 80). Final analysed: Game=39; Control=40.

8. Randomisation and Allocation

Simple randomisation (1:1) using computer-generated list by independent statistician. Group assignment placed in sealed opaque envelopes; opened by researcher immediately before session.

9. Data Collection Procedures

Knowledge test administered on paper. Unique codes used instead of names. Data entered twice into SPSS 20.0; discrepancies resolved by audit.

10. Statistical Analysis Plan (SAP)

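### Ranking the pre-test with the post-teaching scores makes the within-group forgetting contrasts in section 10.2 conservative, by up to about 29% in the standard error if the pre-test is nearly always lowest

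*Combined protocol and SAP*

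**What the plan says.** Section 10.2 of the combined protocol and SAP sits under the heading "10.2. Secondary/Exploratory Analyses". For change over time within each arm it specifies "Friedman two-way repeated measures ANOVA (pre, Day 0, Day 14, Month 7). Post-hoc Dunn-Bonferroni pairwise tests". No other within-group test is named and no standard-error formula is given. Four visits make six pairwise contrasts per arm.

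Three other parts of the document matter:

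- Section 4 excludes students with "Previous theoretical or practical training on breech presentation". This is the only support for expecting a low pre-test; no pre-test mean, SD or within-student correlation is stated.
- Section 2 puts retention as a comparison of arms: "To compare knowledge retention at 14 days and 7 months post-intervention between groups". Section 10.2 tests that aim by "Mann–Whitney U" at Day 14 and Month 7.
- Section 7 reports "Final analysed: Game=39; Control=40" and gives the pilot Day 0 means and SDs (game 40.5, SD 4.2; control 37.8, SD 5.1).

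**The concern.** The contrasts Day 0 v Day 14, Day 0 v Month 7 and Day 14 v Month 7 are the plan's only tests of whether either arm forgets. In the planned procedure their error term depends on a fourth score, the pre-test, which carries no information about forgetting.

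If teaching lifts nearly every student well above the pre-test, the three later scores share ranks 2 to 4 and vary less against one another than the four-visit formula allows. The contrasts are then tested against too large a standard error. The six-fold Bonferroni factor adds to this, since three of the six contrasts are pre v post comparisons that are hardly in doubt. The omnibus Friedman does not help, because a jump from pre-test to Day 0 is enough to reject it.

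The error runs towards finding no significant loss. What is at stake is a modest fall within an arm passing unnoticed and then being described as retained knowledge.

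**Working it through.** **Plan's own figure.** None exists for these contrasts. The only design calculation, in section 7, concerns the Day 0 comparison between arms and does not bear on this point.

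**Inputs from the document.** k = 4 visits and six pairs (section 10.2); n = 39 and 40 (section 7); Day 0 means and SDs (section 7); integer scores from 0 to 47 (section 6).

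**Assumed.** The standard Dunn-after-Friedman standard error; the pre-test level; the correlations; the size of the fall.

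**Standard error.** With k exchangeable visits and no ties, a within-student rank has variance (k² − 1)/12, and two ranks have covariance −(k + 1)/12. The variance of their difference is therefore k(k + 1)/6, and the standard error of a mean-rank difference is √[k(k + 1)/(6n)].

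- As planned, k = 4, n = 39: √(20/234) = 0.292.
- If the pre-test is always lowest, the other three visits behave as k = 3: √(12/234) = 0.226.
- Ratio: √(20/12) = 1.291. At n = 40 the values are 0.289 and 0.224, with the same ratio.

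**Critical values, n = 39.** Two-sided 0.05/6 gives z = 2.638.

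- Planned critical mean-rank difference: 2.638 × 0.2924 = 0.771.
- With the k = 3 standard error and the same six-fold correction: 2.638 × 0.2265 = 0.597.
- Real per-contrast error of the planned test under full separation: 2[1 − Φ(2.638 × 1.291)] ≈ 0.0007, against the nominal 0.0083.

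**How the excess depends on the gain.** Simulated ratio of the formula's standard error to the true one, no forgetting, n = 39, SD 4.7, correlation 0.3 to 0.7, rounded scores with ties:

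| Mean gain from pre-test | Ratio |
|---|---|
| 0 | 1.03–1.05 |
| 3 | 1.06–1.12 |
| 5 | 1.11–1.21 |
| 8 | 1.21–1.33 |
| 12 | 1.30–1.36 |

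The rows include the effect of ties, which is why the first row exceeds 1 and the last exceeds 1.29.

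**Power, Day 0 v Month 7.** Game arm, n = 39, SD 4.2, pre-test mean 22 (SD 5), correlation 0.6 among post-teaching scores and 0.3 with the pre-test, half the fall by Day 14, six-fold Bonferroni for both tests:

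| True fall (points) | Planned Dunn | Paired signed-rank |
|---|---|---|
| 2 | 20% | 65% |
| 2.5 | 45% | 88% |
| 3 | 70% | 97% |
| 4 | about 97% | close to 100% |

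For a 2-point fall with one setting changed:

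- Correlation 0.4: 10% v 44%.
- Lecture arm (SD 5.1, n = 40): 12% v 47%.
- Pre-test mean 30: 26% v 66%.
- Pre-test mean 35: about 40% v 67%.

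With no fall, the signed-rank test rejects in about 0.7% of replicates (nominal 0.83%), so its extra power is not bought with false positives.

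**Splitting the gap.** Dunn on the three post-teaching visits only, still with the six-fold correction, has about 52% power at 2 points. Of the 45 percentage points between 20% and 65%, about 32 therefore come from removing the pre-test from the ranking. About 13 come from the signed-rank test's use of the size of the differences.

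**The case against.** The strongest reply is that little depends on this. The contrasts are within-group and listed as secondary or exploratory. The error is conservative, so it cannot create a false claim of loss. No section says that a non-significant contrast will be read as retention. All of that stands, and it limits the weight of the point.

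A reader might infer three stronger things that the document does not support.

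- *That the 29% is established.* It needs the pre-test to be lowest for essentially every student. The exclusion in section 4 makes a gain plausible but does not fix its size, and the smaller gains in the table give much less.
- *That real knowledge loss is likely to be missed in general.* In the game-arm scenario this holds for falls of about 2 to 2.5 points; at 3 points planned power is already about 70%. With SD 4.7 and correlation 0.5 it is 42% at 3 points and 80% at 4. Day 14 losses are harder to detect: 3% to 14% power at 2 points over correlations 0.3 to 0.7. The document names no loss that matters, so 2 points is an illustration. The nearest yardstick is the 2.7-point difference between arms implied by section 7 (40.5 − 37.8).
- *That the retention aim is compromised.* That aim compares the arms by Mann–Whitney tests, which do not use the Dunn standard error. Nor does the primary Day 0 test.

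Sample size also has a part: at 2 points even the three-visit Dunn test with three-fold Bonferroni has only 28% to 65% power over correlations 0.3 to 0.7 (SD 4.7).

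**Conclusion.** The point holds as one about conservative exploratory contrasts. The planned ranking inflates the standard error for the three post-teaching contrasts by up to about 29% before ties if the pre-test is nearly always lowest, and by roughly 5 to 20% for gains of 3 to 5 points. The cost is power for modest falls and is small for Month 7 falls of 4 points or more in the game-arm scenario. The direction was the same in every scenario examined. The size rests on assumed pre-test levels, correlations and falls that the document does not give. It is worth correcting because the remedy is cheap and these are the only tests of forgetting within an arm.

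**What to change.** For the within-group pairwise contrasts in section 10.2, compute paired Wilcoxon signed-rank tests from each pair's own scores, with Holm correction over the six pairs in each arm. If the three pre v post contrasts are rejected first, Holm leaves multipliers of at most 3 for the other three, which removes most of the multiplicity penalty. An alternative that stays closer to the plan is a Friedman test on Day 0, Day 14 and Month 7 only, with Dunn comparisons among those three visits.

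Follow-up ran to July 2023 (section 3) and the document is dated March 2025. The added tests should therefore appear beside the planned Dunn results, not in place of them, and be labelled as added after data collection. The report should also state that neither the four-visit omnibus nor a non-significant Dunn contrast is evidence of retention.

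The cost is a sentence or two in the SAP and a short rerun on data already held. The one downside is that the signed-rank test assumes roughly symmetric paired differences; a paired sign or permutation test can check that.

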10.3. Assumptions & Checking

- Normality checked via Shapiro–Wilk; non-normal distribution anticipated \Rightarrow non-parametric tests chosen.

10.4. Handling Missing Data

Complete-case analysis. Participants with missing follow-up tests excluded from that specific time-point analysis; no imputation performed (anticipated $< 5\%$ missing).

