10.1. Primary Outcome Analysis

- **Between-group comparison (Day 0):** Mann–Whitney U test.
- Report Median (IQR) & Mean \pm SD.

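### Does the missing-data rule fail for the four-visit Friedman test, and does the under-5% expectation clash with the 10% attrition allowance?

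*Combined protocol and SAP*

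**What the plan says.** Section 10.4 gives the whole missing-data rule in two steps. It first names complete-case analysis, then continues: "Participants with missing follow-up tests excluded from that specific time-point analysis; no imputation performed". It adds an expected amount, "anticipated $< 5\%$ missing", without saying whether that is per visit, per student or overall.

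Three kinds of analysis come under the rule:

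- Primary (section 10.1): "Between-group comparison (Day 0): Mann–Whitney U test".
- Later between-group comparisons (section 10.2): a separate Mann–Whitney test at Day 14 and at Month 7.
- Within-group change (section 10.2, headed secondary/exploratory): "Friedman two-way repeated measures ANOVA (pre, Day 0, Day 14, Month 7"), followed by "Post-hoc Dunn-Bonferroni pairwise tests".

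Section 7 sets recruitment separately: "Allowing 10 % attrition, recruitment target set at 40 per group", starting from 35 per group. It reports 39 and 40 students analysed, without tying those counts to a visit.

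**The concern.** A Friedman test treats each student as a block of four scores and ranks within the block. A student who misses only Month 7 has an incomplete block and leaves the test altogether, taking the observed pre-test, Day 0 and Day 14 scores along. If the Dunn–Bonferroni pairs are run as the follow-up to that test, the student also leaves the pre-test versus Day 0 pair, although both scores exist. Excluding someone from one time point only has no meaning here. The Mann–Whitney tests, by contrast, use everyone present at the visit, so the within-group and between-group results could describe different students without the reader being told.

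Two further points seem to add weight. The low expected missingness is the only support offered for not imputing, and section 7 appears to plan for twice as much. Also, an analysis of those present at Month 7 assumes that absentees resemble returners, although their earlier scores could be used to relax that. If weaker students stayed away, and more so in one arm, the Month 7 comparison would be biased.

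**Working it through.** **1. The attrition allowance.** Inputs from section 7: 35 per group, 10%. Then 35 / (1 − 0.10) = 38.9, rounded up to 39; the plan states 40. This agrees apart from rounding. The actual margin is 1 − 35/40 = 12.5%. (The 35 is taken as given; how it was derived is a separate matter.)

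**2. Are 5% and 10% incompatible?** The 10% is a recruitment margin, the 5% an expected rate of missing tests. If 5% is per visit and absences at Day 14 and Month 7 are independent, the share missing at least one is 1 − 0.95² = 9.75%, so both figures can be true together. If 5% is an overall rate, 10% is simply a more cautious margin. For comparison, inflating 35 for 5% gives 35 / 0.95 = 36.8, or 37, so the larger allowance errs on the safe side. The reported total is 39 + 40 = 79 against a target of 80, a shortfall of 1/80 = 1.25%.

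**3. How many students does the Friedman test lose?** Let m be the share missing at each of k visits, out of 40 per arm. Complete blocks number 40(1 − m) if the same students miss every time, 40(1 − m)^k if absences are independent, and 40(1 − km) if they never overlap.

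| Assumption | Same students | Independent | No overlap |
|---|---|---|---|
| k = 2 (Day 14, Month 7), m = 5% | 38 | 36.1 | 36 |
| k = 3 (all post-tests), m = 5% | 38 | 34.3 | 34 |
| k = 3, m = 2% | 39.2 | 37.6 | 37.6 |

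The k = 3 rows are pessimistic, because Day 0 is tested immediately after the session. On the k = 2 row the loss is 5% to 10% of students. Using section 7's 10% as if it were real dropout gives 0.10 × 40 = 4 students. If each missed one visit, 4 × 3 = 12 observed scores per arm go unused, out of 160 scheduled.

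**4. Which results are affected?** Each Mann–Whitney test uses one visit, so the time-point rule applies to it exactly as written. That covers the Day 0 primary and both later between-group tests. Both aims in section 2 are between-group comparisons. The Friedman test compares visits within an arm and answers neither.

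**5. Possible bias at Month 7.** If non-returners differ from returners by g points in both arms, the shift in the between-group difference is g × (difference in missing share between arms). With g = 4 (assumed) and a 10-percentage-point imbalance, it is 4 × 0.10 = 0.4 points. If missingness is under 5% in each arm, the imbalance is under 5 points and the shift is under 4 × 0.05 = 0.2. If under 5% holds only for both arms combined, 0.4 is a limit approached only when every loss falls in one arm. The assumed 4 points is large: the pooled SD from section 7 is √((4.2² + 5.1²)/2) = 4.67, so 4 / 4.67 = 0.86 SD. The 2.7-point difference in section 7 (40.5 − 37.8) is a Day 0 pilot figure, so it is no yardstick for a Month 7 effect.

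**The case for a change.** The best case for a change is that section 10.4 contains two rules, listwise and available-case, which give different sets as soon as one student misses one follow-up, and nothing assigns either to the Friedman test. Read strictly, the opening words would even remove a Month 7 absentee from the Day 0 primary. Moreover, 10% is attached to a Day 0 calculation, where loss should be lowest, and under 5% to follow-up running to Month 7. A likelihood-based mixed model would use every observed score and need only missing-at-random; a Skillings–Mack test would keep incomplete blocks.

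Part of this stands. The Friedman set is not stated, the 5% has no unit, and no counts by visit are given. The remainder does not carry. The second sentence of section 10.4 itself prevents the strict reading for single-visit tests, and the opening words supply the only workable reading for the four-visit test. Any analyst running a standard Friedman test would restrict it to complete blocks. The Skillings–Mack test would recover a few students in an exploratory test.

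The mixed model is a debatable exchange. It replaces rank tests, chosen in section 10.3 because non-normality was expected, with a normal-residual model on a 0–47 scale where pilot means were 40.5 and 37.8. Using every score while also adjusting for pre-test would make pre-test both outcome and covariate. The document is dated March 2025, after follow-up to July 2023, so the switch would also be post hoc. Such a model, fitted to post-test scores and labelled post hoc, would be a reasonable optional sensitivity analysis.

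**Conclusion.** No change to the plan follows. The mismatch between the time-point rule and the Friedman test is real, but it is a gap in wording that complete-case analysis fills in the obvious way. It is confined to a secondary/exploratory within-group test and costs roughly 2 to 4 of 40 students per arm if 5% miss each of the two later visits. Different numbers at different visits are ordinary in available-case analysis and are dealt with by reporting n at each visit and n with all four scores. The 5% and 10% figures do not conflict.

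The Month 7 bias is hypothetical: under 0.2 points if missingness stays below 5% in each arm and the assumed 4-point gap holds. This rests on the plan's own expectation of low missingness, which the documents neither confirm nor contradict by visit. Heavy, uneven loss at Month 7 would be a concern for the Mann–Whitney comparison there, but it would not arise from the Friedman wording, and clarifying that wording would not cure it.

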10.5. Software

IBM SPSS Statistics v20.0 (Armonk, NY, USA).

10.6. Interim Analysis

None planned; single-session educational intervention with minimal risk.

11. Ethical Considerations

Ethics approval: Kocaeli University Non-Interventional Clinical Research Ethics Committee (28 Jan 2022; GOKAEK-2022/02.11). Study conducted by Declaration of Helsinki. Written informed consent obtained. Data anonymised.

12. Data Monitoring & Safety

Minimal-risk educational study; no independent DSMB. Adverse events unlikely; any unanticipated problems to be reported to ethics committee within 7 days.

13. Administrative Information & Protocol Amendments

All substantial amendments approved by ethics committee and recorded in ClinicalTrials.gov history.
